Official Title: Effect of tetrabenazine on Stroop interference in Huntington disease

NCT: NCT0183491

ID: L-10,830

Document Date: 5/25/2016

Effect of tetrabenazine on Stroop interference in Huntington disease

[name].

Protocol, Statistical Analysis Plan, and Results

Specific Aim

Tetrabenazine has been shown to improve gating of abnormal visual stimuli and improve postural stability in Huntington disease (HD) patients as measured by computerized dynamic posturography testing [1]. This study aims to elucidate whether partial dopaminergic depletion via low dose tetrabenazine has a similar effect on masking out of abnormal visual stimuli on the Stroop interference test.

Background

The effect of tetrabenazine on chorea has been well established [2], Additional effects which may not necessarily involve chorea and may involve improvement in information processing of divergent stimuli have only recently been elucidated [1].

This study investigates whether partial dopaminergic depletion via brief administration of low dose tetrabenazine has a beneficial effect on Stroop scores in Huntington disease patients. Showing an improvement in processing of visual stimuli at a lower dose chorea would be an intriguing possibility, further supporting a separate, chorea-independent mechanism for some of tetrabenazine's beneficial effects. Most likely, this is a dopamine related effect involving information processing in the frontal lobe [1]. Dopaminergic blockade in healthy volunteers with haloperidol has been shown to reduce Stroop interference [3]. Dietary dopaminergic depletion in healthy volunteers also reduced Stroop interference [4].

The study is aimed as a pilot study. If results are promising, a larger trial with longer-term administration of tetrabenazine and more frequent, blinded measurements of Stroop interference during the titration period may be considered.

Analysis of raw scores from Stroop testing in the Huntington Study Group trial [2] showed a statistically significant decline in the raw word reading score, but no significant changes in the raw color reading or raw interference scores. Calculated Stroop scores using either the Golden or Chafetz formulae [5] were not reported for this trial. It may be possible that the Chafetz score would properly account for slower word reading in tetrabenazine treated Huntington disease patients and show reduction in interference even if the raw interference score remains unchanged. For this reason, raw as well as calculated interference scores via both formulae will be reported in this trial. A three day withdrawal of steady state high tetrabenazine by Fekete et al. showed a significant effect on the calculated Stroop test [5].

Methods:

Study design:

Ten subjects who are residents of Terence Cardinal Cooke (TCC) nursing home and have an established diagnosis of Huntington disease will be recruited by the principal investigator for participation in this study. Anticipated breakdown subject numbers by sex or ethnic categories is not known.

Key inclusion criteria for the study will be:

1. Established diagnosis of Huntington disease by movement disorders expert
2. Patients not currently taking tetrabenazine as well as those off tetrabenazine for at least three days will be enrolled
3. Patients should not have taken dopamine receptor blocking medication for at least three days (as this has been shown to affect the Stroop score in normals [3]).

The data collection instrument is the standard Stroop color naming, word reading, and interference test.

Stroop test will be administered to patients in the morning to patients who are OFF tetrabenazine (de novo or three day withdrawal). 12.5 mg of TBZ will be administered just after the first Stroop test and also 3 hours later. ON Stroop test will be administered 6 hours after the OFF Stroop test.

The raw word reading, color reading, and interference scores will be recorded and used for further analysis.

Resources:

The study will be conducted at Terence Cardinal Cooke (TCC) nursing home, which has a dedicated wing exclusively for HD patients. The staff members in the HD unit have years of experience in dealing with the challenges of HD care. In addition, they have years of experience of treating HD with tetrabenazine.

Evaluation:

Statistical analysis:

The three raw Stroop scores will be compared between ON and OFF groups. In addition, both Golden and Chafetz interference scores will be calculated, with customary age correction according to established convention. The ON and OFF scores may be compared using paired Student's t-test in the cases of raw scores and Golden calculated scores. Chafetz scores will be compared via Wilcoxon signed rank test.

Power analysis

Given that a study examining effect on Stroop scores in the setting of low dose tetrabenazine administration has not been previously performed, the size of the potential effect is not known and hence direct power analysis is not possible.

The closest study from which to obtain effect size on Stroop test for power analysis is a three day withdrawal of steady state tetrabenazine [6]. Using Glass's δ formula:

$$d = |\text{average}_a - \text{average}_b| / \text{stdev}_{\text{control}} \quad d = |14.3 - 7.72| / 7.5 = 0.8773$$

alpha=0.05 for single tailed t test power=1-beta error=0.95 with sample size of 8

as calculated by G Power software

Safety monitoring:

The principal investigator will always be reachable in case of side effects. If an untoward side effect such as worsening of depression does occur after the first dose, the patient will be withdrawn from the study. It is expected that frequency and severity side effects will be low given the low dose and brief period of administration of the study drug. It is important to note that the side effects listed in the prescribing information for tetrabenazine were noted during dose escalation towards higher target doses and are aggregates of side effects during multi-week studies.

References

2. Huntington Study Group. Tetrabenazine as antichorea therapy in Huntington disease: a randomized controlled trial. *Neurology* 2006; 66: 366-72.

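### Does the Background's chorea-independent reading oblige this Stroop pilot to record chorea at OFF and ON?

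*Combined protocol and SAP*

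**What the plan says.** The Background begins from the drug's known action: "The effect of tetrabenazine on chorea has been well established". It then turns to "Additional effects which may not necessarily involve chorea and may involve improvement in information processing of divergent stimuli", which it describes as a recent observation, citing earlier posturography work. The key sentence follows: "Showing an improvement in processing of visual stimuli at a lower dose chorea would be an intriguing possibility", with the continuation "further supporting a separate, chorea-independent mechanism for some of tetrabenazine's beneficial effects". Words seem to be missing around the dose in that sentence, so its exact premise cannot be recovered.

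The rest of the plan concerns Stroop. The Specific Aim asks whether low-dose tetrabenazine affects performance on the Stroop interference test. Under Study design, "The data collection instrument is the standard Stroop color naming, word reading, and interference test", and "The raw word reading, color reading, and interference scores will be recorded and used for further analysis". Both doses fall between the OFF test and the ON test, which are 6 hours apart. Under Statistical analysis, "The three raw Stroop scores will be compared between ON and OFF groups", and the Golden and Chafetz scores are compared as well. On the calculated scores, the Background says only that "It may be possible that the Chafetz score would properly account for slower word reading in tetrabenazine treated Huntington disease patients". Neither the design nor the analysis mentions a chorea or motor rating.

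**The concern.** The Background attaches a mechanistic meaning to a positive result, and the plan collects nothing that bears directly on it. The drug is acknowledged to act on chorea and is given between the two tests, so chorea could change over the same 6 hours as the Stroop scores. A low dose is not in itself evidence that chorea was unchanged, and the documents supply no such evidence. If interference fell, the dataset could not distinguish a Stroop gain with stable chorea from one with reduced chorea.

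The Chafetz score may allow for slower reading, but it does not measure chorea. The cited healthy-volunteer studies are indirect. At stake is one inference: a reader might take a Stroop improvement as support for chorea-independence when this trial had not examined chorea. The Stroop comparison itself is not at stake.

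**Working it through.** The plan gives no figure for chorea, so there is none to reproduce. Its power statement concerns Stroop and does not enter here. Two checks are needed.

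**Does anything in the plan depend on the chorea argument?**

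| Part of the plan | Content | Uses chorea? |
|---|---|---|
| Specific Aim | Effect on Stroop interference | No |
| Study design: instrument and data | Stroop test, three raw scores | No |
| Statistical analysis | Raw, Golden and Chafetz scores, ON against OFF | No |
| Power analysis | Stroop effect from an earlier withdrawal study | No |
| Background | Conditional remark on mechanism | Yes |

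Only the Background remark depends on it. No endpoint, test or decision rule does.

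**Would a chorea rating at each test answer the question?**

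Inputs: n = 10 from Study design, and n = 8 from the Power analysis as a lower case. The documents give neither the low-dose effect on chorea nor its variability, so results are in SDs of the paired differences.

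1. Half-width of the two-sided 95% interval for a mean paired change = t(0.975, n − 1)/√n.
   - n = 10: 2.262/3.162 = 0.715 SD
   - n = 8: 2.365/2.828 = 0.836 SD
2. Power of a two-sided paired t-test at alpha 0.05, by the noncentral t distribution, for a true change of 0.5 SD at n = 10. The noncentrality is 0.5 × 3.162 = 1.58, and the power is 0.293. A simulation of 200,000 runs gave 0.295.
3. True change needed for 80% power: 0.996 SD at n = 10, and 1.156 SD at n = 8.

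Even if the observed mean change in chorea were exactly zero, the interval at n = 10 would run from −0.72 to +0.72 SD. A sizeable fall would remain compatible with the data. In the other direction, an observed fall larger than 0.72 SD would put zero outside the interval. That would weaken the chorea-independent reading but not refute it, since one drug may affect chorea and interference by separate routes.

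**What do the documents say about the rival explanation?**

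That explanation requires chorea relief to improve Stroop interference, and nothing in the documents says that it does. The Background reports that in the cited antichorea trial raw word reading declined, while raw color and raw interference scores did not change significantly. This lends the rival no support on raw scores. It is not decisive, because calculated scores were not reported and a non-significant change is not an absent one.

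**The case for a change.** The strongest case for a change is that the chorea-independent reading is the only meaning the document gives to a positive result beyond the Stroop effect itself. On this view a plan should either collect the data its interpretation needs or withdraw the interpretation. A bedside rating at two existing test times looks inexpensive, and it could expose a large fall in chorea that the present plan would miss entirely.

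Much of this stands. The plan has no direct evidence on chorea, and a large fall would be worth knowing about. Three things keep it from requiring a change:

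- The wording presents the reading as a possibility, adding support to an idea already attributed to other work. The plan does not list it as a conclusion the trial will draw.
- The rating lies outside the trial's own question. With no control group, no blinding and a fixed OFF-then-ON order, even the Stroop change could not be cleanly attributed to the drug, and a chorea change would share that weakness.
- The alternative, deleting or softening a Background sentence, leaves every score, comparison and result as it was.

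It might also be argued that the gap would pass into a later trial. The Background says only that a larger trial may be considered. That trial's measurements are not designed here, so nothing can be concluded about them.

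**Conclusion.** The observation is true but minor, and no change to the plan follows. This trial could support chorea-independence only indirectly, and a careful reader should treat it as a hypothesis the pilot does not test. The Stroop aim and analysis are unaffected.

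The omission amounts to 0 of 20 possible chorea ratings. Its effect on the inference cannot be quantified, because the documents give no low-dose chorea effect. Filling the gap would yield a descriptive change known to within about 0.72 SD at n = 10 (0.84 SD at n = 8), which could reveal a large fall but could not show independence. These precision figures assume a rating from every patient and roughly normal paired differences.

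The Results section reports two patients and no statistical analysis, so the mechanistic inference was never drawn. That limits the practical consequence. The conclusion rests on the plan itself, in which nothing planned depends on the remark.

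### Three interference scores are tested ON versus OFF with no primary score and no multiplicity rule, and the stated power of 0.95 at n = 8 does not follow from the stated effect size.

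*Combined protocol and SAP*

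**What the plan says.** The Specific Aim concerns "masking out of abnormal visual stimuli on the Stroop interference test". The Background puts the question more broadly, as whether the drug "has a beneficial effect on Stroop scores in Huntington disease patients".

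The Statistical analysis section compares the three raw scores (word reading, color reading, interference) between ON and OFF, and then: "In addition, both Golden and Chafetz interference scores will be calculated". Raw and Golden scores may be compared by paired t-test; Chafetz scores go to the Wilcoxon signed-rank test. The section gives no alpha, no side, no order of testing and no primary score.

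The Background explains why several scores are kept. Tetrabenazine may slow word reading, and the Chafetz score might then "show reduction in interference even if the raw interference score remains unchanged". It commits that "raw as well as calculated interference scores via both formulae will be reported in this trial". On next steps it says: "If results are promising, a larger trial" may be considered. It does not define promising.

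The Power analysis section takes its effect from a three-day withdrawal study, computes d = |14.3 − 7.72| / 7.5 = 0.8773, and states power 0.95 for a single-tailed t-test at alpha 0.05 with n = 8. It does not say which Stroop score these values are. Study design plans for ten: "Ten subjects who are residents of" the nursing home. Results reports that two enrolled and that no statistical analysis was possible.

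**The concern.** The construct in the aim is measured three ways, and the plan itself foresees that the raw and Chafetz scores may point differently. With no primary score, such a split has no planned reading: one reader could call the pilot promising on Chafetz, another could call it negative on raw interference, and both would be following the plan. If any one favourable score is enough, the chance of going forward on noise exceeds the nominal 5%.

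The side matters too. The analysis section is silent, and the one-tailed statement in the power paragraph is made for a t-test, so it does not expressly cover the signed-rank test. Nor does either section say which direction of change in each score is favourable.

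The power statement belongs with this point because choosing a primary score fixes the test and the sample size to which the power must refer. The existing statement is for n = 8 rather than the planned 10, and for an unnamed score.

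**Working it through.** **1. Effect size.** Inputs from Power analysis: |14.3 − 7.72| / 7.5 = 6.58 / 7.5 = 0.8773. This reproduces.

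**2. Stated power.** For a one-tailed paired t-test at alpha 0.05, power = P(T > t(0.95, n − 1)), where T is noncentral t with n − 1 degrees of freedom and noncentrality dz·√n. Using d directly as the standardized paired difference (dz = 0.8773):

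| n | critical t | noncentrality | power |
|---|---|---|---|
| 8 | 1.895 | 2.481 | 0.722 |
| 10 | 1.833 | 2.774 | 0.819 |
| 15 | 1.761 | 3.398 | 0.943 |
| 16 | 1.753 | 3.509 | 0.955 |

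So 0.95 at n = 8 is not reproduced; on this reading it needs n = 16.

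**3. What would give 0.95.** Glass's formula divides by the standard deviation of the scores, not of the paired differences. With equal ON and OFF standard deviations, dz = d / √(2(1 − ρ)), where ρ is the ON/OFF correlation, so ρ = 1 − (d/dz)²/2. Step 2 corresponds to ρ = 0.5.
- n = 8: 0.95 needs dz = 1.299, so ρ = 1 − (0.8773/1.299)²/2 = 0.772.
- n = 10: 0.95 needs dz = 1.131, so ρ = 1 − (0.8773/1.131)²/2 = 0.699.

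The document gives no ON/OFF correlation.

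**4. Power at n = 10, one-tailed, by assumed ON/OFF correlation.** Signed-rank figures are simulated with normal differences and the exact critical value (actual level 0.042).

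| ρ | dz | paired t | signed-rank |
|---|---|---|---|
| 0.3 | 0.741 | 0.698 | 0.646 |
| 0.5 | 0.877 | 0.819 | 0.773 |
| 0.7 | 1.133 | 0.951 | 0.928 |
| 0.8 | 1.387 | 0.991 | 0.985 |

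No row belongs to a particular score, because the document does not say which score d came from.

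**5. False-positive chance over three interference scores.** Assumed rule: any one score at p < 0.05 counts as promising. If the scores were independent, 1 − 0.95³ = 0.143. For equally correlated normal statistics (2,000,000 simulations):

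| correlation between scores | one-sided | two-sided |
|---|---|---|
| 0 | 0.142 | 0.142 |
| 0.5 | 0.118 | 0.125 |
| 0.7 | 0.103 | 0.109 |
| 0.9 | 0.080 | 0.084 |
| 0.95 | 0.071 | 0.073 |

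Repeating this at n = 10 with the planned mix (two paired t-tests and one exact signed-rank test) gives 0.136 down to 0.072 one-sided and 0.141 down to 0.079 two-sided, so small-sample behaviour changes little. The correlations between scores are assumptions too. The calculated scores are built from the same readings as the raw ones, so zero correlation is implausible.

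**The case against.** This is a self-described pilot of ten patients. Success means only that a larger trial may be considered, and nothing confirmatory rests on a p-value. The plan explains why it uses several scores, commits in advance to reporting all the interference scores, and assigns a test to each. That removes most of the room for selective reporting. Alpha and side are stated in the paragraph after the analysis text. Two patients enrolled, so no inference was drawn. All of this stands, and it keeps the point modest. What remains is that reporting every score does not say which one answers the aim, and the plan itself expects disagreement.

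Three stronger readings are tempting and should be resisted.

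- *That the power paragraph makes Golden the implied primary.* A reader might combine its t-test with the Background remark that the withdrawal study "showed a significant effect on the calculated Stroop test". But the plan assigns the t-test to raw interference as well. The Background remark also cites reference 5, which is the scoring paper, while Power analysis cites reference 6. Nothing identifies the score behind 14.3 and 7.72.
- *That the error rate is 14%.* That is the independence limit under a decision rule the document does not contain.
- *That 0.95 is unattainable at these sample sizes.* It is attainable if the ON/OFF correlation is high enough; the document simply does not state or justify one.

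**Conclusion.** The point holds as a planning gap of moderate weight. Three tests address the aim, with no primary score, no multiplicity rule, and no side or alpha in the analysis section. Under the assumed any-one-score rule, the false-positive chance is about 7% to 14% for correlations between scores from 0.95 down to 0, more likely in the lower part of that range.

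The power statement is unsupported as written. With d as the paired effect it is 0.72 at n = 8 and 0.82 at n = 10. To keep 0.95 for the t-test, an unstated ON/OFF correlation of about 0.77 (n = 8) or 0.70 (n = 10) would have to be justified, assuming equal standard deviations. Every score-specific power figure, for Golden as much as for Chafetz, is illustrative.

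A reader might infer that the trial's conclusions are compromised. They are not: no test was run. The gap matters for any reuse of this plan.

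**What to change.** Before any analysis under this plan:

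1. Name the Chafetz score as the single primary. It is the score the Background's rationale about slower word reading supports.
2. Test it once, by the planned signed-rank test at one-sided 0.05, and state in the analysis section the side and which direction of change is favourable.
3. Say that promising is judged on that score.
4. Report raw interference, Golden, word reading and color reading as secondary, with paired differences and 95% confidence intervals.
5. Correct the power statement: either restate it for n = 10, or state and justify the ON/OFF correlation assumed. Name the score behind 14.3 and 7.72 in either case. For the signed-rank test at n = 10, power is about 0.77 if the same d applies as a paired effect; say that it may not apply if d came from another score.

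This takes a few sentences and no new data. The costs are that a significant result on another score alone could not be claimed, and that the stated power falls unless a high ON/OFF correlation can be justified. The signed-rank test itself gives up about 0.05 in power against the t-test at n = 10 (0.773 against 0.819), if differences are normal.
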